27. PROVISIONS TO PROTECT THE PRIVACY INTERESTS OF SUBJECTS

All study activities will be conducted in a private setting. The collection of sensitive information about subjects is limited to the information necessary to conduct the research study. Subjects will be told that they can skip any question they wish.

28. COMPENSATION FOR RESEARCH-RELATED INJURY

This research presents minimal risk. No funds have been set aside for compensation.

29. ECONOMIC BURDEN TO SUBJECTS

None.

30. CONSENT PROCESS

Informed consent will be obtained. All members of the research team will be trained in Human Subjects and the handling of data to ensure confidentiality in order to obtain Institutional Review Board (IRB) approval from UMass Chan. Participants will be appropriately consented. This will include a clear understanding of the study objectives and procedures, content of the survey protocols that will be administered, and ample opportunity to have their questions answered, and prior to the surveys. Participation will be on a voluntary basis, and we will obtain written consent from participants after the detailed explanation of the study and opportunity to ask questions. The consent process for participation in the study will occur in-person. All research personnel will be research personnel will be familiar with HRP-090: Informed Consent Process for Research.

31. PROCESS TO DOCUMENT CONSENT IN WRITING

INVESTIGATOR STUDY PLAN - REQUIRED

Consent for study participation will be done in writing. All research personnel will be familiar with HRP-091: Written Documentation of Consent. The consent form will require a signature from the participant. The participants' signatures will be obtained at the one time in-person visit.

Appendix A. Copies of the messages

** Before seeing each message, participants will view one of the four directions below according to their assigned source condition.*

Condition	Expert		Peer	
	Expert 1 Government health org	Expert 2 Medical school researcher	Peer 1 Young adults	Peer 2 Influencers
Directions	Imagine that the following message was written by scientists.	Imagine that the following message was written by your doctor.	Imagine that the following message was written by young adults like you.	Imagine that the following message was written by a social media influencer that you follow.

Messages with Sidedness Manipulation

One-sided	Two-sided
Sleek design hides a deadly truth. Vapes contain ingredients that can cause cancer.	Vapes come in sleek design that makes them look cool. But these designs hide a deadly truth. Vapes contain ingredients that can cause cancer.
That's not "just vapor." Vapes have ingredients that cause lung disease and cancer.	Vape companies say that you're vaping "just vapor." But that's not true. Vapes have ingredients that cause lung diseases and cancer.
You wouldn't drink formaldehyde. Why would you vape it? Most vapes have formaldehyde.	Some people say that vaping isn't bad for you. But most vapes have formaldehyde. You wouldn't drink formaldehyde. Why would you vape it?
Trouble breathing? Vape flavors may cause lung damage.	Vapes come in cool flavors that make you keep wanting to use. But these flavors may cause you lung damage and trouble breathing.
Chemicals in these vape flavors can hurt your lungs.	Cinnamon roll, very vanilla. Mmm...sounds tempting, but chemicals in these vape flavors can hurt your lungs.
Chemicals in these vape flavors can cause cell and lung damage.	Sugar and spice and everything nice? NOPE. Chemicals in vapes can cause cell and lung damage.
Depression? What a vibe check. People who keep vaping are more likely to have signs of depression.	People vape for cool vibes. But people who keep vaping are more likely to have signs of depression. What a vibe check.

INVESTIGATOR STUDY PLAN - REQUIRED

Vaping causes coughing and lung damage. Not a good look.	Influencers may make vaping look cool, but the coughing caused by lung damage? Not a good look.
The lung damage caused by vaping will never be cool.	Vaping is going viral, but you know what will never be cool? The lung damage caused by vapes.
Extra salty lately? That might be nicotine withdrawal. Vape addiction is REAL.	Some people vape to get in a good mood. But are you extra salty lately? That might be nicotine withdrawal. Vape addiction is REAL.
Chained to your vape? Nicotine addiction means losing your independence.	Adult smokers are vaping to stop being addicted to cigarettes. But you can get addicted to vaping. It means being chained to your vape and losing your independence.
Vaping companies create catchy terms for nicotine addiction. Hard pass.	"JUUL Buzz"? That's a catchy term. But that just means nicotine addiction. Hard pass.
Don't get hooked by the flavors. Some pods have as much nicotine as a whole pack of cigarettes.	It's easy to get hooked by the flavors. But it's a sham. Some pods have as much nicotine as a whole pack of cigarettes.
Some pods contain as much nicotine as 20 cigarettes. Don't get hooked by the flavors.	Think you're just vaping flavor? Some pods contain as much nicotine as 20 cigarettes. Don't get hooked.
Nicotine addiction won't give you much of a choice. Most vape products contain nicotine. Don't get hooked.	The flavors may be limitless, but nicotine addiction won't give you much of a choice. Most vape products contain nicotine. Don't get hooked.
Do your friends get salty if they haven't had a hit? That's nicotine addiction. JUUL pods contain nicotine - as much as a pack of cigarettes.	It may be fun to get that perfect hit with your friends. But do your friends get salty if they haven't had a hit? That's nicotine addiction. JUUL pods contain nicotine - as much as a pack of cigarettes.
Vaping with friends leads to fighting with friends. Nicotine addiction makes people moody and hard to be around, which really kills the vibe.	Vaping can give you and your friends a good vibe at first. But it can soon lead to fighting. Nicotine addiction makes people moody and hard to be around, which really kills the vibe.
You'll be hooked forever. Don't trade nicotine addiction to be on trend.	It may be today's big thing, but you'll be hooked forever. Don't trade nicotine addiction to be on trend.

INVESTIGATOR STUDY PLAN - REQUIRED

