11. PROCEDURES INVOLVED*

After providing informed consent, participants will be randomized to one of four experimental conditions in a 2 (Source: expert and peer) x 2 (Presentation: one-sided and two-sided) design. Data will be collected through iMotions, a psychophysiological data collection platform. We will track participants' eye movements using an eye-tracking device. We will assess heart rate and skin conductance with a sensor by attaching Velcro-strapped electrodes on the fingers of participant's nondominant hand. When the study begins, participants will complete pretest measures, view messages, during which they will be measured on their psychophysiological responses, and complete posttest measures. Messages (see Appendix-A) will be presented in a random order for at least 10 seconds. Between each message segment, a black screen and "get ready" screen will be presented for 10 seconds to return participants' heartrate and skin conductance levels to baseline. This meets the established amount of time (6 seconds) to collect heart rate and skin conductance.⁴⁵ This procedure will be repeated 18 times for the 18 messages. Finally, participants will complete measures on demographics, attitudes, and behavioral intentions. The entire procedure will take approximately 45 minutes. After completion, participants will be thanked and compensated \$50 for participation. Participants will be extensively debriefed about the hypothetical nature of the message source, the health harms of using any tobacco product, and information about the Massachusetts Tobacco Quitline with contact information. We will provide a consent form and verbally reiterate this information.

In order to minimize subject harm as a result of being shocked by static electricity from the sensors, room temperature will remain above 65 degrees when running participants as the colder,

INVESTIGATOR STUDY PLAN - REQUIRED

drier air is more likely to cause static shock. We will also follow all safety guidelines for the equipment. These include having participants wash their hands thoroughly, then use hand sanitizer, and then use an alcohol towelette to clean the finger the sensor will be placed. In addition, participants will be instructed to try to keep their hand still during the study to ensure the sensor does not move.

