Cover Page for ClinicalTrials.gov

Document:

Statistical Analysis Plan

Official Study Title:

Responses to Message Source and Presentation Using Psychophysiology

Document Date:

January 17, 2024

Psychophysiological Testing

Study Design and Power Analysis:

We will assess which communication principles influence psychophysiological responses on visual attention, orienting response, and arousal to determine the features that can increase acceptance of e-cigarette education messages in young adults. Eligible participants will be randomly assigned to one of four experimental conditions in a 2 (Source: expert and peer) x 2 (Presentation: one-sided and two-sided) design. For the psychophysiological part of the Aim 1, we will recruit total 112 young adults (age 18 to 24) vapers and susceptible non-vapers. We will use stratified sampling, with n=56 for each vaping status. The estimation was based on Stevens et al.'s (2021) study. Based on simulations as in crowdsourcing study, participants per message condition gave stable ranks for the top 3 messages. We use a conservative approach and propose 7 participants per the message condition for each vaping status. I will use a multi-attribute decision-making (MADM) framework to produce a dataset containing data on participant response to each message with source + presentation type. I will merge crowdsourced and psychophysiological data to rank messages and determine optimal content. This technique has been used in our previous work. MADM provides a practical, transparent framework for considering data across multiple inputs, determining the relative importance of each attribute, and simultaneously evaluating detail at the attribute level and in a summary measure across all attributes using aggregate data.

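### In 3 to 6 of the 18 Appendix A message pairs the negative claim changes along with sidedness, so version differences in those pairs cannot be attributed to sidedness alone

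*Protocol*

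**What the plan says.** Protocol section 11 randomizes participants in a "2 (Source: expert and peer) x 2 (Presentation: one-sided and two-sided) design" and states "This procedure will be repeated 18 times for the 18 messages". Section 5 describes a two-sided message as one that gives the negative health effects of vaping and also acknowledges possible reasons for vaping. The example there has the same harm clause in its one-sided and two-sided forms.

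Appendix A lists the texts under a heading that calls them a sidedness manipulation. The pairs are not numbered; the numbers used here follow their order. The two-sided text of pair 8, for example, reads "Influencers may make vaping look cool, but the coughing caused by lung damage? Not a good look".

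Section 10 names harm perceptions and message acceptance among the primary outcomes. Section 13 averages heart-rate change per theme, treats skin conductance similarly, compares dwell time by theme category, and ranks messages on mean self-report scores. The SAP plans a dataset on "participant response to each message with source + presentation type", to be merged with crowdsourced data to rank messages and find the best content.

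Neither document describes a check that the harm content is equal within pairs, or an analysis that allows for differences.

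**The concern.** Aim 1 asks which presentation type works best. That requires the two versions of a message to differ in presentation and in little else. If the two-sided text also changes what is said to cause the harm, how many harms are asserted, or how firmly, then the version contrast mixes sidedness with a different claim. Harm perception is an outcome, so the added ingredient bears directly on what is measured. Randomization balances people between conditions but cannot remove a difference built into the stimuli.

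The exposure is greatest at message level. The SAP justifies its group size by the stability of the ranks of the top three messages, and an altered pair is not diluted there by the other pairs. If one-sided pair 8 outranked its partner, the explicit causal statement alone could be the reason.

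**Working it through.** **Count of pairs.** Appendix A contains 18 pairs, which agrees with the 18 messages in section 11.

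**Comparison within pairs.**

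| Pair | One-sided | Two-sided | What changes |
|---|---|---|---|
| 6 | "Chemicals in these vape flavors can cause cell and lung damage" | Same damage, attributed to chemicals in vapes | The agent: flavors to vapes |
| 8 | "Vaping causes coughing and lung damage. Not a good look" | Concedes the pull of influencers, then puts the cough down to damaged lungs with no cause given for the damage | The statement that vaping causes the harm is dropped |
| 11 | Nicotine addiction costs you your independence | "Adult smokers are vaping to stop being addicted to cigarettes. But you can get addicted to vaping", then the chained and lost-independence wording | Nicotine addiction becomes addiction to vaping |
| 4 | Trouble breathing is posed as a question; only lung damage is asserted | Lung damage and trouble breathing are both asserted | One more asserted harm |
| 17 | Vaping with friends *leads to* fighting | It *can soon lead to* fighting | Certainty |
| 12 | "Vaping companies create catchy terms for nicotine addiction. Hard pass" | A brand term is called catchy but said to mean nicotine addiction | Blame on companies replaced by a brand term; the harm is the same |

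Smaller wording shifts in pairs 2, 9 and 14 are not counted.

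**Share of pairs.**
- Clear changes (6, 8, 11): 3/18 = 17%.
- Adding 4 and 17: 5/18 = 28%.
- Adding 12 on the strictest reading: 6/18 = 33%.

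**Effect on the pooled contrast.** If the altered claim in pair j shifts the version difference by d_j, the mean over 18 pairs shifts by (sum of d_j)/18. The documents give no d_j. As an illustration only, assume every d_j has the same sign and a size of 0.3 to 0.8 SD:
- 3 pairs: 3/18 × 0.3 = 0.05 to 3/18 × 0.8 = 0.13 SD.
- 6 pairs: 6/18 × 0.3 = 0.10 to 6/18 × 0.8 = 0.27 SD.

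These are upper limits for each assumed size, since shifts of opposite sign would partly cancel. Pair 8 arguably weakens the causal claim, while pair 6 widens the agent.

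**Cost of leaving pairs out.** Assume a person SD of 1 and a message residual SD s of 1 to 2, with each person seeing one version of each message, as in section 11. The ratio of standard errors of a person's mean with k pairs rather than 18 is sqrt[(1 + s²/k)/(1 + s²/18)].
- k = 13, s = 1: sqrt(1.0769/1.0556) = 1.010. With s = 2: sqrt(1.3077/1.2222) = 1.034.
- k = 12, s = 1: sqrt(1.0833/1.0556) = 1.013. With s = 2: sqrt(1.3333/1.2222) = 1.044.

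Section 26 instead describes each participant seeing both versions, 36 messages in all. The person's own level then cancels from the contrast and the loss is larger, at most sqrt(18/13) = 1.18 or sqrt(18/12) = 1.22.

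**Length.** The two-sided text is longer in 18 of 18 pairs: 402 words against 246, a ratio of 1.63 (means 22.3 and 13.7). The ratio is 1.54 without pairs 4, 6, 8, 11 and 17, and 1.55 when 12 is also left out. Dropping the altered pairs therefore leaves the length difference in place.

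**The case against.** The strongest defense is that section 5 does not require the harm sentence to be carried over word for word. It asks only that a two-sided message present harm and acknowledge reasons, and its example happens to keep the clause. The main planned output is a ranking of texts, and a ranking of the texts as shown stays valid whatever differs between them. No pair-by-pair version test is specified, and several physiological measures are averaged by theme. All of this stands. It limits the concern to attribution, but Aim 1 does attribute results to presentation type.

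Four stronger readings are tempting and not supported:
- A reader might infer that the whole sidedness comparison is uninterpretable. On this ground it is not: 12 to 15 of the 18 pairs keep the harm claim.
- A reader might count pair 12 as a changed harm. Both versions name nicotine addiction; only the target of blame changes. It belongs in a stricter variant.
- A reader might treat the adult-smokers line in pair 11 as a changed harm claim. That line is the acknowledgement, and so the intended manipulation. The change that counts is the loss of nicotine as the object of addiction.
- A reader might want to delete *these* from the one-sided texts of pairs 5 and 6 because no flavor is named. In pair 5 the harm clause is the same in both versions, and the deletion would unmatch it. Appendix A shows text only, so whether the displayed stimulus gave the word a referent cannot be judged.

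**Conclusion.** The point holds in limited form. The negative claim changes with sidedness clearly in pairs 6, 8 and 11, and also in pairs 4 and 17; pair 12 is borderline. The count rests on a judgment about what makes up the harm claim, so it should be stated as a range and not as one figure. In the affected pairs, a version difference or a difference in rank mixes sidedness with altered content. The size and sign of the resulting error in the pooled contrast are unknown. This is a matter for a planned sensitivity analysis and careful wording of conclusions. It is not a reason to discard the comparison.

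**What to change.** Keep the texts and the analysis of all 18 pairs. Before analysis, list pairs 4, 6, 8, 11 and 17 as altered, with pair 12 added in a stricter variant. Report the one-sided versus two-sided comparison for all 18 pairs, without the five (13 left), and without the six (12 left). State in advance that a version difference within a listed pair will not be attributed to sidedness.

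Do not reword the messages for this purpose. The SAP merges these results with crowdsourced data, and if the same texts were used there, edits would break the match.

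The cost is one additional analysis in two variants. Under the between-person layout and the assumed SDs, the standard error of a person's mean rises by about 1% to 3.4% with 13 pairs and 1.3% to 4.4% with 12. It rises by more if each person sees both versions.

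The report should also state as a limit that two-sided texts are longer in every pair. This matters most for dwell time, and leaving out the altered pairs does not cure it.

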Appendix-C.

Dear [NAME],

My name is [NAME] and I am a research staff at the UMass Chan psychophysiological lab. We're still looking for participants to participate in a lab study to examine the psychophysiological responses (eye-movement, heart rate, skin conductance) of e-cigarette education messages. If you are interested, please fill out the screener. A member of our research team will be in touch with you if you are eligible for our study. Thank you for your interest!

Thank you!
Research Staff Name

INVESTIGATOR STUDY PLAN - REQUIRED

eIRB Section 7.0 Attachments Upload Checklist

Follow [How to Manage Files in eIRB](#) and upload the following items as applicable to your submission. This checklist is provided for your convenience and is not a requirement for review.

Investigator Study Plan
Sponsor protocol
Research portion of the grant
Human subjects portion of the grant
Written approvals from ancillary reviews (Clinical Engineering, COI, IBC, PRC, RSC, Students as Subjects, etc.)
Recruitment materials such as flyers, brochures, posters, scripts of radio ads, etc.
Data collection sheets, case report forms, etc.
Surveys, measures, instruments, etc.
Measures to assess capacity to consent
DMC or DSMB charter
Data safety monitoring plan
Adverse event log
Investigator brochure or package insert for drugs
Instructions for use or approved FDA labeling for devices
Sponsor justification or FDA documentation for non-significant risk device study
IND or IDE documentation
Patient information sheet for Humanitarian Use Device
Approval order for Humanitarian Use Device
Product labeling for Humanitarian Use Device
HIPAA waiver
HIPAA authorization
Authorization to contact form
Consent form(s)
Assent forms(s)
Fact sheet(s)
Multi-site communication plan
Study staff training plan
SOPs or Manuals of Operations
Screening log
Compensation log
Certificates of translation or translator attestations
Data use agreements, memoranda of understanding,
Documentation of data/specimen anonymity (i.e., provider will never break the code)

Cover Page for ClinicalTrials.gov

Document:

Statistical Analysis Plan

Official Study Title:

Responses to Message Source and Presentation Using Psychophysiology

Document Date:

January 17, 2024

Psychophysiological Testing

Study Design and Power Analysis:

We will assess which communication principles influence psychophysiological responses on visual attention, orienting response, and arousal to determine the features that can increase acceptance of e-cigarette education messages in young adults. Eligible participants will be randomly assigned to one of four experimental conditions in a 2 (Source: expert and peer) x 2 (Presentation: one-sided and two-sided) design. For the psychophysiological part of the Aim 1, we will recruit total 112 young adults (age 18 to 24) vapers and susceptible non-vapers. We will use stratified sampling, with n=56 for each vaping status. The estimation was based on Stevens et al.'s (2021) study. Based on simulations as in crowdsourcing study, participants per message condition gave stable ranks for the top 3 messages. We use a conservative approach and propose 7 participants per the message condition for each vaping status. I will use a multi-attribute decision-making (MADM) framework to produce a dataset containing data on participant response to each message with source + presentation type. I will merge crowdsourced and psychophysiological data to rank messages and determine optimal content. This technique has been used in our previous work. MADM provides a practical, transparent framework for considering data across multiple inputs, determining the relative importance of each attribute, and simultaneously evaluating detail at the attribute level and in a summary measure across all attributes using aggregate data.

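### Seven participants per message condition is not shown to give stable top-3 ranks for the psychophysiological outcomes, and the planned ranking carries no measure of uncertainty

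*SAP*

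**What the plan says.** The SAP's section on design and power gives two grounds for the sample size. One is a published study ("The estimation was based on" a 2021 reference). The other is simulation: "Based on simulations as in crowdsourcing study, participants per message condition gave stable ranks for the top 3 messages". It continues: "We use a conservative approach and propose 7 participants per the message condition for each vaping status". The total is stated as "we will recruit total 112 young adults (age 18 to 24) vapers and susceptible non-vapers", split as "We will use stratified sampling, with n=56 for each vaping status".

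No variance, definition of stable, alpha, power or effect size is given for any outcome.

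On use of the data, Protocol section 13 (Data Analysis and Management) averages heart-rate change by theme and looks for the greatest deceleration. It treats skin conductance in a similar way, reads dwell time by theme category, and ranks messages on self-report means. The SAP then merges crowdsourced and psychophysiological data in a multi-attribute decision-making (MADM) framework to rank messages and settle on the optimal content. Neither document mentions an interval, a resampling step or a probability for any rank.

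**The concern.** Protocol section 10 lists psychophysiological responses among the primary outcomes, and the Background gives 112 as the size of the in-lab study that measures them. The assurance offered for that size is that the top 3 ranks are stable. Rank stability depends on how far the messages truly differ relative to the noise in the outcome. Nothing in the documents gives that ratio for heart rate, skin conductance or dwell time, so the reader cannot tell whether the assurance carries over to them.

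The deliverable is a choice of best messages. A bare ranking always produces a top 3, whether the differences are real or noise. If stability is weak, a repeat of the study could recommend different messages, and nothing in the planned report would show it.

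**Working it through.** **Step 1: the stated total.** Total = participants per condition × conditions × vaping groups.

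- The SAP describes participants as "randomly assigned to one of four experimental conditions in a 2 (Source: expert and peer) x 2 (Presentation: one-sided and two-sided) design". With those four conditions: 7 × 4 × 2 = 56, not 112.
- Protocol Appendix A has two expert and two peer directions: "participants will view one of the four directions below according to their assigned source condition". Four directions × two presentation types = 8 message conditions, and 7 × 8 × 2 = 112. This reproduces the total.
- If the cells are the four of the 2 × 2, then 112 / (4 × 2) = 14 per cell.

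The check below therefore uses both n = 7 and n = 14. The 7 itself cannot be reproduced, because the simulation inputs and the stability criterion are not given.

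**Step 2: inputs for an illustration.**

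- Number of messages: 18, from Protocol section 11 ("This procedure will be repeated 18 times for the 18 messages").
- n: 7 or 14, from step 1.
- Residual SD per participant and message: set to 1 (scale only).
- Between-message SD: r. **Assumed**, because the documents give no value. Share of within-condition variance due to true message differences = r² / (r² + 1).

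**Step 3: model.** True message means are drawn from N(0, r²). Each is observed with error variance 1/n; a participant's overall level cancels because each participant rates every message in the condition. The observed top 3 is compared with the true top 3.

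Chance benchmarks: exact set 1 / C(18,3) = 1/816 = 0.12%; average overlap 3/18 = 17%.

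**Step 4: results.**

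| r | Share of variance | Exact top 3, n = 7 | Overlap, n = 7 | Exact top 3, n = 14 | Overlap, n = 14 |
|---|---|---|---|---|---|
| 0.2 | 0.04 | 2% | 37% | 4% | 45% |
| 0.5 | 0.20 | 14% | 60% | 24% | 68% |
| 1.0 | 0.50 | 37% | 76% | 50% | 82% |
| 1.5 | 0.69 | 52% | 83% | 63% | 87% |

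Example of the share: r = 1.5 gives 2.25 / 3.25 = 0.69.

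**Step 5: what 7 would need.** Average overlap of 80% takes about 11 participants per condition at a share of 0.5 and about 5 at 0.7. Seven falls between, so it reaches that level only when true message differences exceed about half of the within-condition variance.

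**Step 6: repeatability.** If stable means that a second sample of the same size gives the same top 3, the n = 7 figures are lower: about 0.5%, 5%, 23% and 39% at r = 0.2, 0.5, 1.0 and 1.5.

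**The case against.** Several points on the other side stand.

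- **Source of the simulation.** A reader might infer that the 7 comes from crowdsourced ratings alone. The documents do not support that. The wording can mean the same simulation method rather than the same data, and the 2021 study is a second ground whose type of outcome is not described. The most that can be said is that no psychophysiological input is shown.
- **The word conservative.** A reader might conclude that it is false. It cannot be tested: the number of participants the simulations supported does not appear in the text available, possibly through extraction. Nor does any passage say that 112 was chosen for feasibility.
- **Planned use of the physiology.** The illustration ranks single messages on one noisy outcome. The protocol averages heart rate by theme, and the final ranking merges crowdsourced data across attributes. Both could reduce noise, so the percentages are not error rates for the final ranking.
- **Assumed signal.** Nothing places these outcomes at the low end of r. At r = 2 and 3, overlap at n = 7 is 87% and 91%. Exact recovery is also a strict criterion that the SAP does not adopt, and overlap of 60% is well above the 17% expected by chance.

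These points limit the claim but do not remove it. The SAP's stability statement is about messages, the protocol ranks messages on self-report means, and no MADM weights are given. The stability of the merged ranking is therefore undemonstrated too.

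**Conclusion.** The point holds in a limited form: 7 per message condition is not shown to be adequate for the psychophysiological outcomes, and the ranking is planned without uncertainty. It would go too far to say that 7 has been shown to fail, since that depends on a signal-to-noise ratio the documents do not give.

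The size is conditional. Over r = 0.2 to 1.5, exact recovery of the top 3 runs from about 2% to 52% at n = 7 and from about 4% to 63% at n = 14. This assumes 18 messages, one outcome, normal effects, and no theme averaging or merge. The absence of rank uncertainty rests on no assumption; it follows directly from the analysis text.

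**What to change.** 1. In the SAP, either give the simulation inputs for each psychophysiological outcome (variances, stability criterion, number of participants supported and result) or state that top-3 stability has not been established for these outcomes. Say what conservative is measured against.
2. State whether the 7 refers to four or eight conditions, so that it agrees with 112.
3. Bootstrap participants within vaping status and condition, resample the crowdsourced participants as well, and carry each resample through the theme averaging and the MADM merge.
4. Report a rank interval and a top-3 probability for each message or theme, and call a message optimal only with that probability beside it.

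The cost is a few restated sentences and one resampling analysis, with no extra participants. The bootstrap will be coarse in cells of 7 to 14, and the stated assurance may become less favourable.
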